5.7.4 Use in Nursing Women

It is unknown whether pembrolizumab is excreted in human milk. Since many drugs are excreted in human milk, and because of the potential for serious adverse reactions in the nursing infant, subjects who are breast-feeding are not eligible for enrollment.

5.8 IMRT

IMRT will be delivered in 30 fractions over 6 weeks (five fractions per non-holiday week) in one plan (SIB) to a total dose of 60-66Gy. Missed treatments due to holidays or logistic reasons can be compensated for by delivering an additional BID treatment during the week, OR treating on the Saturday or Sunday of that week, OR adding to the end of treatment.

5.8.1 Immobilization and Simulation

Patients must have an immobilization device (e.g. Aquaplast mask) made prior to treatment planning CT scan. Use of an immobilizing mouthpiece is optional as clinically indicated.

It is preferable to perform treatment planning CT scan with IV contrast if nodal regions or skull base will be targeted and there are no medical contraindications to the use of contrast. The treatment planning CT scan must be performed with the immobilization device and in the treatment position. Slice thickness should be 0.3 cm or thinner.

5.8.2 Target Delineation

There should be no Gross Tumor Volume (GTV). The Clinical Target Volume (CTV₆₀) is defined as the tumor and/or lymph node bed that was dissected. All patients must have a CTV₆₀. There are two optional CTVs that can be used. Elective areas deemed at risk of subclinical disease that have not been dissected (e.g. elective nodes) can be treated to a lower dose of 54Gy (CTV₅₄). For areas of highest risk, such as positive margins, or extranodal extension, a high risk CTV (CTV₆₆) can be used to focally boost these areas in a simultaneous fashion. This treatment volumes should be kept as small as possible.

The Planning Target Volume (PTV₆₀) should be a 3mm expansion around CTV₆₀. If additional CTV's are used, they should have their own PTV (e.g. CTV₅₄ →PTV₅₄) with a 3mm margin. In general, as the skin is the origin of disease, it will often be targeted. In these cases, the PTV should be allowed to extend outside of the external skin surface and 5mm of custom bolus must be used. When the skin is not part of the target, then the PTV can be shaved out of skin by 3-5mm to enhance planning capabilities.

All plans must be normalized such that 95% of the volume of the PTV₆₀ is covered with prescription dose of 60 Gy. Additionally: At 1 cc PTV1 volume on the DVH curve, the dose should not be > 110% of the prescribed dose. At a volume of 0.03 cc within the PTV₆₀ volume on the DVH curve, the dose should not be < 95% of the prescribed dose. For any volume of tissue outside the PTVs that has a size of 1 cc, the dose should not be > 70 Gy.

Elective treatment of lymph nodes is at the discretion of the treating radiation oncologist, and will be determined on a case by case basis. In general, for tumors of the scalp, if lymphatics are targeted, they should include: occipital, parotid, anterior cervical (levels 2-4), and posterior cervical (level 5) nodes. When targeting lymph nodes for tumors of the face (e.g. nose, cheek, temple, eyelid, lip): parotid, anterior cervical (levels 2-4), and submandibular (level 1B) should be included. For ear tumors, pre and post-auricular nodes should be included in addition to parotid, anterior cervical (levels 2-4), and posterior cervical nodes.

For patients with perineural invasion of named nerves, these nerves should be included in the elective CTV₅₄ to their origin of the skull base. For those with extensive involvement or

proximal involvement adjacent to the skull base, the involved nerves should be targeted back to the respective nerve ganglion (e.g. Meckel cave for the Gasserian ganglion of the trigeminal nerve).

5.8.3 Critical Normal Structures

The normal tissue volume to be contoured will depend on the site of origin of the cancer. In general, they will include the brainstem, spinal cord, cochlea mandible, glottic larynx, supraglottis, constrictors, esophagus, trachea, oral cavity, lips and parotid and submandibular salivary glands that are not at risk. For tumors of the scalp and other requiring treatment of the skull base, the following should also be included: eyes, lenses, optic nerves, optic chiasm, pituitary, hypothalamus. The PRV (planning risk volume) spinal cord contours will be defined at least 0.5 cm larger in the radial dimension than the spinal cord (*i.e. the cord diameter on any given slice will be 1.0 cm larger than the cord itself*).

5.8.4 Treatment Planning and Delivery

Megavoltage energy photon beam irradiation is required. Static beam intensity modulation or volumetric arc based planning are acceptable for planning.

5.8.5 Image Guidance for IGRT

IGRT with daily conebeam CT is required recommended. If a cone beam CT is not available, portal images should be used. Region-of-Interest (ROI) or “clip box” for fusion should be set to encompass the high dose PTV and adjacent spinal cord. When the skull base is targeted, the globes and optic nerves should routinely be included, if possible, for alignment purposes. Following the registration, the translational and (if the appropriate technology is available) rotational corrections should be applied to the treatment couch. If all the variances are less than 10 mm (this typically corresponds to one half of the usual PRV margin), the treatment can proceed with appropriate corrections; however, re-imaging is not mandatory. If one or more of the corrections are larger than 10 mm, the imaging must be repeated in addition to performing table/positioning adjustments. However, the use of numerous repeat IGRT studies should be avoided (see next section).

5.8.6 Definition of Normal Tissues/Organs at Risk (OARs)

NOTE: Only the parts of the normal tissues/organs at risk outside the PTVs will be considered for dose optimization purposes. Only those OAR that are in proximity to the

treatment volume must be contoured. Contouring OAR that are far from the treated area and will receive negligible doses is unnecessary.

Spinal Cord: The cord begins at the cranial-cervical junction (i.e. the top of the C1 vertebral body). Superior to this is brainstem and inferior to this is cord. The inferior border of the spinal cord is at approximately T3-4 (i.e., just below the lowest slice level that has PTV on it). The spinal cord shall be defined based on the treatment planning CT scan. In addition, however, a Planning Risk Volume (PRV) spinal cord shall be defined. The PRV_{cord} = cord + 5 mm in each dimension. This is irrespective of whether or not IGRT is used.

Brainstem: The inferior most portion of the brainstem is at the cranial-cervical junction where it meets the spinal cord. For the purposes of this study, the superior most portion of the brainstem is approximately at the level of the top of the posterior clinoid. The brainstem shall be defined based on the treatment planning CT scan. In addition, however, a Planning Risk Volume (PRV) brainstem shall be defined. The PRV_{brainstem} = brainstem + 3 mm in each dimension.

Lips and Oral Cavity: These should be contoured as 2 separate structures as the goal is to keep the lip dose much lower than the oral cavity dose. The definition of lips is self-explanatory. The oral cavity will be defined as a composite structure consisting of the anterior 1/2 to 2/3 of the oral tongue/floor of mouth, buccal mucosa, and palate.

OARpharynx/constrictors: This will be defined as the “uninvolved” posterior pharyngeal wall plus adjacent constrictor muscles. This extends from the superior constrictor region (the inferior pterygoid plates level) to the cricopharyngeal inlet (posterior cricoid cartilage level).

Cervical Esophagus: This will be defined as a tubular structure that starts at the bottom of OARpharynx and extends to the thoracic inlet.

Glottic/Supraglottic Larynx (GSL): This will be defined as a “triangular prism shaped” volume that begins just inferior to the hyoid bone and extends to the cricoid cartilage inferiorly and extends from the anterior commissure to include the arytenoids. This includes the infrahyoid but not suprahyoid epiglottis.

Mandible: This includes the entire boney structure of the mandible from TMJ through the symphysis.

Other structures (self explanatory): Optic Nerves, optic chiasm, orbits, lenses, cochlea, lacrimal glands, parotid glands, submandibular glands

Unspecified Tissue Outside the Targets: This will be defined as tissue located between the skull base and thoracic inlet that is not included in either the target volumes or the normal tissues described above.

5.8.7 Dose Prescription

Doses to PTVs

See Section 5.8.2 above for definitions of CTVs and PTVs and their prescribed doses. The goal is for 95% of the PTV60 to receive ≥ 2 Gy with a minimum dose (cold spot) of no less than 54 Gy. It is recognized that portions of the PTV60 close to the skin may receive significantly less than 54 Gy if it is not deliberately targeted with custom bolus applied. This is acceptable as long as cold spots within PTV60 do not exist at a depth deeper than 8 mm beneath the skin. For PTV_66, when used, 95% of the volume should get the prescription dose, and <0.03cc should receive >110% of the dose. This criteria does not apply for PTV_54 when used.

Doses to Normal Structures

Spinal Cord: The PRVcord should not exceed ≤ 50 Gy to any volume in excess of 0.03 cc (approximately 3 mm x 3 mm x 3 mm). In treatment planning, the spinal cord PRV should be given the highest priority.

Brainstem: The brainstem should not exceed 56 Gy to any volume in excess of 0.03 cc (approximately 3 mm x 3 mm x 3 mm). The PRVbrainstem (brainstem +3mm) should be limited to 60Gy. These can be exceeded in cases where the tumor abutted the brainstem and was resected. Max point dose to the brainstem can never exceed 62Gy.

Optic Nerves and Chiasm: These should be limited to a max dose of 54Gy.

Orbits: Should be limited to a max dose of 50Gy with 95% <45Gy. These doses may be exceeded when the tumor is abutting the globe preoperatively and is adjacent to the postoperative bed. The max dose to 0.03cc of the globe can never exceed 52Gy.

Lacrimal Gland: This should be limited to a mean <30Gy whenever possible. This may be exceeded when the tumor location approximated this structure preoperatively and is subsequently at risk or adjacent to the tumor bed.

Lips: Reduce the dose as much as possible. The mean dose should be < 20 Gy when possible.

Oral Cavity: Reduce the dose as much as possible. The mean dose should be < 30 Gy when possible.

Parotid Glands (not targeted): In most cases, it will be easier to spare one parotid than the other. The treatment planning goal will be for this individual parotid gland to receive a mean dose of <26 Gy.

Submandibular gland (not targeted): If level Ib is not a target, aim to reduce mean contralateral submandibular gland to < 39 Gy.

OARpharynx/constrictors: Reduce the dose as much as possible. Some recommended (but not mandatory) treatment goals include: 1) No more than 33% of the OARpharynx exceeds 50Gy; 2) Mean dose < 45 Gy; 3) No more than 15% of the OARpharynx exceeds 60 Gy.

Cervical Esophagus: Reduce the dose as much as possible. Some recommended (but treatment goals include: Mean dose < 30 Gy.

Glottic and Supraglottic larynx (GSL): Reduce the dose as much as possible. The glottic larynx mean dose is recommended to be ≤ 25 Gy.

Mandible: Reduce the dose as much as possible. Hot spots within the mandible should be avoided. It is recommended that maximum dose within the mandible be < 66 Gy, except in areas overlapping PTV.

Unspecified Tissue Outside the Targets: No more than 1cc of unspecified tissue outside the targets can receive 70 Gy or more

5.8.8 Radiation Therapy Treatment Interruptions

Treatment interruptions are strongly discouraged. Treatment breaks must be clearly indicated in the treatment record when they occur. Patients who have treatment interruptions in radiation for >3 weeks will be taken off study. The interruption of radiation therapy for grade 4 mucositis / dermatitis / dysphagia is at the discretion of the treating radiation oncologist. Treatment breaks, if necessary, ideally should not exceed five treatment days at a time and ten treatment days total. Treatment breaks should be allowed only for resolution of severe acute toxicity and/or for intercurrent illness and not for social or logistical reasons. Pembrolizumab will not be administered during radiotherapy treatment breaks.

5.9 Subject Withdrawal/Discontinuation Criteria

Subjects may withdraw consent at any time for any reason or be dropped from the trial at the discretion of the investigator should any untoward effect occur. In addition, a subject may be withdrawn by the investigator or the Sponsor if enrollment into the trial is inappropriate, the trial plan is violated, or for administrative and/or other safety reasons. Specific details regarding discontinuation or withdrawal are provided in Section 7.1.4 – Other Procedures.

A subject must be discontinued from the trial for any of the following reasons:

- The subject or legal representative (such as a parent or legal guardian) withdraws consent.
- Confirmed radiographic disease progression
- Unacceptable adverse experiences as described in Section 7.2
- Intercurrent illness that prevents further administration of treatment
- Investigator's decision to withdraw the subject
- The subject has a confirmed positive serum pregnancy test
- Noncompliance with trial treatment or procedure requirements
- The subject is lost to follow-up
- Administrative reasons

The End of Treatment and Follow-up visit procedures are listed in Section 6 (Protocol Flow Chart) and Section 7.1.5 (Visit Requirements).

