5.5.2 Prohibited Concomitant Medications

Subjects are prohibited from receiving the following therapies during the Screening and Treatment Phase (including retreatment for post-complete response relapse) of this trial:

- Antineoplastic systemic chemotherapy or biological therapy
- Immunotherapy not specified in this protocol
- Chemotherapy not specified in this protocol
- Investigational agents other than pembrolizumab
- Live vaccines within 30 days prior to the first dose of trial treatment and while participating in the trial. Examples of live vaccines include, but are not limited to, the following: measles, mumps, rubella, varicella/zoster, yellow fever, rabies, BCG, and typhoid vaccine.
- Systemic glucocorticoids for any purpose other than to modulate symptoms from an event of clinical interest of suspected immunologic etiology. The use of physiologic doses of corticosteroids may be approved after consultation with the Sponsor.

Subjects who, in the assessment by the investigator, require the use of any of the aforementioned treatments for clinical management should be removed from the trial. Subjects may receive other medications that the investigator deems to be medically necessary.

The Exclusion Criteria describes other medications which are prohibited in this trial.

There are no prohibited therapies during the Post-Treatment Follow-up Phase.

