7.1.1.7 Subsequent Anti-Cancer Therapy Status

The investigator or qualified designee will review all new anti-neoplastic therapy initiated after the last dose of trial treatment. If a subject initiates a new anti-cancer therapy within 30 days after the last dose of trial treatment, the 30 day Safety Follow-up visit must occur before the first dose of the new therapy. Once new anti-cancer therapy has been initiated the subject will move into survival follow-up.

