8.0 STATISTICAL ANALYSIS PLAN

8.1 Study Design

This is a phase II trial evaluating the addition of concurrent and adjuvant fixed-dose pembrolizumab in combination with standard IMRT, in order to establish safety and estimate efficacy of this regimen to be tested in a subsequent randomized registration trial. At the conclusion of the study, the primary safety endpoint will be proportion of DLT. The primary efficacy endpoint will be 1-year PFS. Progression-free survival (PFS) will be calculated from treatment initiation to disease progression or death from any cause or last follow up.

8.2 Justification of Design and Sample Size:

The target sample size will be 34 patients. Assuming a <10% drop out or ineligibility rate, 37 patients will be enrolled to ensure 34 evaluable patients (all evaluable patients will be analyzed). The sample size was generated based on the primary safety endpoint. DLT $\leq 20\%$ is acceptable and $\geq 40\%$ is unacceptable. If 11 or more of 34 patients experience DLT, this regimen will be considered too toxic. The significance level and power of this design are 6% and 86%, respectively. If 8 or fewer patients experience DLTs, the regimen will be deemed safe to proceed for further study. If 9 or 10 patients experience DLTs, the PI will examine the type, reversibility and duration of DLTs and a careful decision will be made whether to pursue this regimen further in this adjuvant population.

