8.3 Statistical Analysis Plan

DLT will be estimated using an exact 95% confidence interval. If 11 or more patients experience DLT the regimen will be considered too toxic. One-year PFS will be estimated using the Kaplan-Meier method and a 95% confidence interval constructed using Greenwood's method. One year PFS outcomes will be assessed overall and also separately for immunocompetent patients vs. immunosuppressed patients (e.g. CLL). These outcomes will be compared to our historical dataset for both subsets respectively. Adverse events will be tabulated by category and grade. The rates of

adverse events will be estimated using an exact 95% confidence. The relationship between 1yr PFS and baseline PD-L1 expression will be assessed using logistic regression. Immunoprofiles in peripheral blood in serial samples will be tested using random effects ANOVA. Bioinformatic analysis will be applied to all genomic and transcriptomic data.

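### Exit rules that take patients off study, with PFS ending at last follow-up, may censor 1-year PFS informatively

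*Combined protocol and SAP*

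**What the plan says.** Four places in the protocol turn an event on treatment into an exit from the study or from disease follow-up.

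- Section 5.9: "A subject must be discontinued from the trial for any of the following reasons". The list includes unacceptable adverse experiences, intercurrent illness that prevents treatment, and noncompliance. It also includes confirmed radiographic progression, which is a PFS event and does no harm here.
- Section 5.8.8: "Patients who have treatment interruptions in radiation for >3 weeks will be taken off study".
- Section 5.5.2: during screening and treatment, subjects who "require the use of any of the aforementioned treatments for clinical management should be removed from the trial".
- Section 7.1.1.7: "Once new anti-cancer therapy has been initiated the subject will move into survival follow-up".

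At early discontinuation, section 7.1.3.1 asks for the final-visit activities once, plus follow-up of adverse events that are present. For details, 5.9 points to a section 7.1.4 on other procedures, but 7.1.4 is headed Visit Requirements and refers only to the flow chart.

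In the statistical plan, PFS "will be calculated from treatment initiation to disease progression or death from any cause or last follow up" (8.1), and "One-year PFS will be estimated using the Kaplan-Meier method" (8.3). Section 8 has no other censoring rule, no definition of an evaluable patient, and no sensitivity analysis for early exit. On numbers, 8.2 says: "Assuming a <10% drop out or ineligibility rate, 37 patients will be enrolled to ensure 34 evaluable patients".

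**The concern.** Kaplan-Meier treats a censored patient as having the same future risk as those still followed. The exits above are unlikely to be random with respect to prognosis. Section 5.8.8 allows radiotherapy breaks only for severe acute toxicity or intercurrent illness, so a break over 3 weeks selects patients who are unwell and whose radiotherapy was interrupted. The first surveillance imaging falls at week 20, after the last pembrolizumab dose at week 16. A patient removed during treatment may therefore contribute no disease imaging beyond what is done at exit.

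What is at stake is the primary efficacy estimate. Sections 2.1 and 8.3 compare 1-year PFS with historical data, and 2.1 makes a favourable comparison part of the signal for a randomized trial. If leavers do worse than stayers, the trial estimate is too high for that comparison.

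**Working it through.** **1. The plan's own figures.** The only design calculation is the DLT rule in 8.2 (too toxic at 11 or more of 34; 20% versus 40%). Exact binomial: P(X ≥ 11 | 34, 0.20) = 0.0620 and P(X ≥ 11 | 34, 0.40) = 0.8617, which match the stated 6% and 86%. The allowance is 37 − 34 = 3 patients, and 3/37 = 8.1%, consistent with below 10%. No expected or historical 1-year PFS is given, so there is no PFS figure to reproduce. The PFS levels below are assumptions.

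**2. How many might leave.** The documents do not say. The nearest figure is the chemoradiation pilot in 4.2.2: 27 − 21 = 6 of 27 (22%) did not complete pembrolizumab, 3 of 27 (11%) because of immune-related events. On 34 patients, 22% is 34 × 6/27 = 7.6 and 11% is 34 × 3/27 = 3.8. Drug non-completion is not trial exit, so I use 10% (close to the plan's allowance) and 22% (an upper-range proxy).

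**3. Size of the bias.** Assumptions: exponential PFS; 1-year PFS *S* in stayers; a fraction *f* of those event-free at week 10 (*t* = 10/52 = 0.192 year) leaves and is censored; leavers then have hazard ratio *HR*; none of their later events is recovered.

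- Kaplan-Meier limit: *S*
- PFS with full follow-up: *S*^t × [(1 − f) × *S*^(1−t) + f × *S*^(HR(1−t))]
- Bias: f × *S*^t × [*S*^(1−t) − *S*^(HR(1−t))]

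Example with *S* = 0.70, *f* = 0.10, *HR* = 2: 0.10 × 0.934 × (0.750 − 0.562) = 0.018, or +1.8 points.

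| PFS in stayers | Leaving | HR 0.5 | HR 1 | HR 2 | HR 3 |
|---|---|---|---|---|---|
| 60% | 10% | −1.4 | 0 | +2.0 | +3.4 |
| 70% | 10% | −1.1 | 0 | +1.8 | +3.1 |
| 80% | 10% | −0.8 | 0 | +1.3 | +2.4 |
| 60% | 22% | −3.0 | 0 | +4.5 | +7.4 |
| 70% | 22% | −2.4 | 0 | +3.9 | +6.7 |
| 80% | 22% | −1.7 | 0 | +2.9 | +5.3 |

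(Bias in percentage points.)

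**4. The same in patients.** Suppose 34 patients and 10 events by one year. Full follow-up gives 24/34 = 70.6% (95% CI 55.3 to 85.9). Let the leavers be censored before week 20.

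| Leave | Events lost | Kaplan-Meier 1-year PFS |
|---|---|---|
| 3 | 1 of 10 | 22/31 = 71.0% |
| 3 | 3 of 10 | 24/31 = 77.4% |
| 8 | 2 of 10 | 18/26 = 69.2% |
| 8 | 4 of 10 | 20/26 = 76.9% |
| 8 | 6 of 10 | 22/26 = 84.6% |

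The estimate moves up only when leavers carry more than their share of events. With 8 leaving and 2 of the 10 events lost, it falls slightly.

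**The case against.** The strongest reply is that the protocol loses less than its exit wording suggests.

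- Stopping the drug is not leaving the trial. Section 5.2.1.2 skips doses, and Table 3 stops pembrolizumab, without cancelling the week 20, 32 and 52 visits. A reader might infer that any treatment stop ends PFS follow-up. The documents do not support that, although one column of Table 3 is ambiguously headed as discontinuing the subject.
- Some events would be recovered. Section 5.9 refers to follow-up visit procedures, 7.1.5.3 permits telephone contact on disease and survival status, survival follow-up captures deaths, and 10.6 brings in registry recurrence data for patients in both studies.
- The prohibited-therapy rule covers only screening and treatment, and it exempts steroids for suspected immune events.
- New anti-cancer therapy in an adjuvant trial may often follow a recurrence that already counts as an event.
- Bias of a few points is small beside a confidence interval of about ±15 points in the example above.

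These points stand and limit the size. They do not close the gap. Telephone contact is optional, registry data cover only mutual patients, neither replaces scheduled imaging, and no text requires imaging after an exit under 5.9, 5.8.8 or 5.5.2. Sampling error is reported in the interval; this bias is not.

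A reader might also infer that toxicity exits could be dropped from the DLT count. Section 4.2.3.2 largely answers this. DLTs count by occurrence through 30 days after the last administration, and the list includes toxicity that prevents completion of IMRT within 8 weeks. A break over 3 weeks in a 6-week course would normally exceed that (6 + 3 = 9 weeks). Only the undefined term *evaluable* in 8.2 stays open.

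**Conclusion.** The point holds in conditional form. Followed as written, the exit rules and the PFS definition can censor 1-year PFS informatively, and section 8 does nothing to detect or limit it.

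That PFS will be inflated is a tempting conclusion, but the documents give no prognosis for leavers, so the direction is not established. If leavers have two to three times the hazard of stayers, the estimate is too high by about 1 to 3 points with 10% leaving and about 3 to 7 points with 22% leaving. At equal hazard there is no bias. At half the hazard the estimate is too low by about 1 to 3 points. These sizes rest on assumed PFS of 60–80% in stayers, exit at week 10, and no recovery of later events. The 22% is drug non-completion under a different regimen and should be read as an upper-range figure. Because no historical PFS value is stated, it cannot be said whether a bias of this size would change the go-forward decision. The change is cheap and should be made.

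**What to change.** The change concerns follow-up and analysis only. No treatment-stopping rule needs to alter.

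- **Sections 5.9, 5.8.8, 5.5.2 and 7.1.1.7:** state that patients who meet these criteria, or who start new therapy without documented progression, remain in study follow-up. They keep the scheduled week 20, 32 and 52 disease assessments until progression, death or withdrawal of consent to follow-up. Correct the cross-reference in 5.9.
- **Section 8, PFS:** count progression or death after treatment stop or new therapy as a PFS event.
- **Section 8, analysis sets:** include every treated patient in the DLT and PFS analyses. The DLT cut-offs are stated out of 34, so say how they apply if more are treated.
- **Section 8, sensitivity analysis:** repeat 1-year PFS counting early exits as events. In the example with 8 exits and 4 events lost, this gives 20/34 = 58.8% against 76.9%; with 3 exits and 1 event lost, 22/34 = 64.7% against 71.0%.

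The cost is protocol wording, a few visits already in the schedule for patients off treatment, and a PFS estimate that may be slightly lower.
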